## 5.2.8 Study Treatment Discontinuation Criteria

RXC004 dose interruption and stopping criteria are detailed in Table 4

**Table 4 Module 1 Dose Interruption and Stopping Criteria**

Event	Action
Diarrhoea	Treat as per Diarrhoea/Colitis Management and Treatment Guidelines
1st incidence of diarrhoea $\geq$ grade 2 (suspected RXC004 related):	Please refer to Appendix 5 Temporarily interrupt RXC004 for up to 14 days*. Consider restarting at lower dose if resolved to $<$ grade 1
2nd occurrence of $\geq$ grade 2 diarrhoea	Temporarily interrupt RXC004 for up to 14 days*. Consider restarting at lower dose if resolved to $<$ grade 1
3rd occurrence of $\geq$ grade 2 diarrhoea	Permanently discontinue study treatment
Bone events	
Confirmed RXC004 related fragility bone fracture (excluding grade 1 vertebral deformities)	Permanently discontinue study treatment
Patients with a DXA scan showing $\geq$ 7% worsening in BMD at lumbar spine or total hip compared to baseline	Permanently discontinue study treatment
An individual increase in $\beta$ -CTX of $\geq$ 350pg/ml from the baseline (screening) value or in individual measurement of $\geq$ 1000pg/ml	Permanently discontinue study treatment unless the patient has received clinical benefit (investigator assessment) and continued treatment is warranted.
Hepatic events	
Grade 3 increases in ALT or AST or ALP ( $>$ 5 x ULN if baseline normal, $>$ 5 x baseline, if baseline abnormal)	Permanently discontinue study treatment
Grade 2 increases in ALT or AST or ALP ( $>$ 3 x ULN if baseline normal, $>$ 3 x baseline, if baseline abnormal) with the appearance of symptoms associated with a clinical diagnosis of hepatitis including right upper quadrant pain or tenderness, fever, rash or eosinophilia ( $>$ 5%)	Permanently discontinue study treatment

Event	Action
Grade 2 increases in ALT or AST (> 3 x ULN if baseline normal, >3 x baseline, if baseline abnormal) and total bilirubin > 2 x ULN or INR* > 1.5 or other evidence of impairment to the synthesis function of the liver]	Permanently discontinue study treatment
*Unless patient is receiving warfarin	
Other adverse events	
Grade 3-4 toxicity (1 st event ^ )	Interrupt RXC004 (max. 14 days*), resume at the next lowest dose level when resolved (grade ≤ 2 or returns to baseline).
Grade 3-4 toxicity (subsequent events ^ )	Permanently discontinue study treatment
Grade < 3 toxicity (all events ^ )	Decision to interrupt RXC004 (max. 14 days*) is at the Investigator's discretion. Resume at same dose prior to interruption.
^ Excluding diarrhoea	
Surgery	Interrupt RXC004 (max. 14 days*), resume at full dose. RXC004 should be stopped 3 days prior to surgery and resumed approx. 10 days later. If the wound has not healed a further 7 days are permitted prior to re-starting RXC004 at the discretion of the Investigator and with approval of Sponsor Physician.  No stoppage is required for biopsy procedures.
Vomiting	If vomiting occurs shortly after RXC004 is swallowed, the dose may be replaced if all of the intact capsules can be counted. Resume with the following scheduled dose.
Missed dose	Allowed to take the scheduled dose up to 4 hours after the scheduled dose time. If greater than 4 hours, the missed dose should not be taken and patient should continue with next dose at allotted time.

Event	Action
Corticosteroid use	
Patients receiving corticosteroids for treatment of diarrhoea should hold RXC004 (for max. 14 days*) as per Diarrhoea/Colitis Management and Treatment Guidelines (please refer to Appendix 5)
 
Patients receiving corticosteroids for any indication other than diarrhoea, should continue RXC004 at current dose level.
 
Patients who require on-study oral or intravenous (i.v.) glucocorticoids for > 4weeks at daily doses equivalent to <math>\geq 7.5</math> mg of oral (p.o.) prednisolone (for any indication other than diarrhoea) should temporarily interrupt RXC004 (for a maximum of 14 days*) if receiving clinical benefit (in the opinion of the investigator) and resume at full RXC004 dose once the daily corticosteroid dose equivalent falls to <7.5 mg PO prednisolone.
 
RXC004 should be permanently discontinued for patients who require on-study oral or intravenous (i.v.) glucocorticoids for > 4weeks at daily doses equivalent to <math>\geq 7.5</math> mg of oral (p.o.) prednisolone and are not receiving clinical benefit from RXC004 (in the opinion of the investigator)

\* RXC004 interruptions of greater than 14 days may be allowed for patients judged by investigator to be clinically benefiting from study treatment, and only after consultation with Sponsor

The dose of RXC004 must not be adjusted under any other circumstances unless prior agreement is given by the Sponsor. All dose modification and interruptions (including any missed doses) and the reasons for the modifications/interruptions are to be recorded in the CRF.

### 5.2.9 Biomarker Samples

An archival or a newly acquired tumour biopsy will be requested from every patient enrolled in the study. Archived/newly acquired biopsies are optional (but encouraged) in the Module 1 dose escalation.

Optional Skin biopsies to assess downstream markers of Wnt expression may be taken from all consenting patients in Module 1. (see Appendix 1 Schedule of Assessments).

In all patients participating in the study, the taking of non-mandatory tumour biopsies will be encouraged and can be taken from each patient at up to 3 time points during the study;

1. At baseline (prior to first dose of RXC004)
2. During RXC004 dosing (see SoA for biopsy timings)

At the time of tumour biopsy, blood samples for assessment of PK and blood borne biomarkers will be taken; Analysis of these samples will include, but not be restricted to, PORCN/Wnt status and functional PORCN/Wnt inhibition, e.g. phosphorylation and/or expression of downstream markers.

### **5.2.10 Exploratory Assessments**

Plasma and PBMC pharmacodynamic samples (all sites) will be obtained at C0D1 (prior to first dose) and at C1D8, C1D15, Day 1 of each cycle thereafter and treatment discontinuation. These samples may be used to examine gene and protein expression changes, including measurement of inflammatory markers. Fresh whole blood (from selected sites of close proximity) will be obtained at C0D1 (prior to first dose), and pre-dose at C1D8, C1D15 and C2D1. Fresh whole blood may be stained for cell surface markers to identify immune cell populations present in the circulation before and after treatment. Circulating tumour DNA (ctDNA) will be collected pre-dose at C0D1 and post-dose on C2D1, C4D1 and at treatment discontinuation. Analysis of total amounts and/or tumour mutations (including Wnt pathway aberrations) in ctDNA samples may be evaluated and correlated to patient response.

## **5.3 Module 2 – RXC004 and Nivolumab Combination**

Based on the safety profile observed to date, a decision has been made by Redx and the SRC to start Module 2.

The reason for conducting this study module is to provide the first cancer patient safety and tolerability data with RXC004 in combination with nivolumab.

Module 2 will commence by enrolling patients with advanced solid tumours into a SAD/MAD monotherapy dose escalation arm. Eligible participants will be enrolled in dose-escalation cohorts treated with RXC004 given as an oral capsule dose in combination with a PD1 infusion. The dose of nivolumab will be a fixed dose of (480 mg every 4 weeks, and will remain at this dose level throughout the study. The dose of RXC004 will be escalated. The RXC004 starting dose for combination with nivolumab will be a lower dose than the highest confirmed safe and tolerated dose from the monotherapy study (Module 1). The RXC004 dose will be dose-escalated to the MTD in combination in as few dose-cohorts as possible. The RXC004 dose

used in Module 2 will not be escalated to exceed the MTD for RXC004 in monotherapy (2mg RXC004 QD).

Patients will take a single dose of RXC004 to evaluate single dose PK, then start on continuous RXC004 dosing up 3-7 days later in combination with nivolumab every 28 days (Cycle 1).

Each cycle will be 28 days from Cycle 1, Day 1.

Dose increments will be guided by safety data observed during Cycle 1, as well as on-going assessment of safety beyond Cycle 1 in earlier cohorts, plus PK and pharmacodynamic data as available. Every new dose cohort will be evaluated for the occurrence of a DLT during Cycle 0 or Cycle 1 of treatment. (Figure 5)

[figure not shown]
Patients will have the option to have their tumour tissue (primarily from an archival source) tested for genetic aberrations (including upstream Wnt pathway aberrations such as RNF43 mutations and RSPO-fusion) by next generation sequencing (NGS) or MassArray technologies.

RXC004 will be administered orally in combination with anti PD1 infusion in patients with advanced solid malignancies. There will be escalation of the RXC004 dose in each cohort with intensive safety monitoring to ensure the safety of the patients. The design of this Module 2 also allows the RXC004 & anti-PD1 combination tolerability and PK to be characterised in an unselected population of patients.

**Figure 5      Module 2 dose escalation**

### **3+3 SAD/MAD design**

#### **Escalation of RXC004 with fixed dose of Nivolumab (480mg)**

### **5.3.1 Module 2 Objectives**

The objectives are detailed in Section 1.9

### **5.3.2 Module 2 Eligibility Criteria**

#### ***5.3.2.1 Module 2 Specific Inclusion Criteria***

The core inclusion are detailed in Section 2.1.1. There are no Module 2 specific inclusion criteria. Patients must fulfill all of the core inclusion criteria in order to be eligible to receive study treatment in Module 2.

#### ***5.3.2.2 Module 2 Specific Exclusion Criteria***

The core and Module 2 specific exclusion are detailed in Sections 2.2.1 and 2.2.2 respectively. Patients must not receive study treatment in Module 2 if any of the Core or Module 2 specific exclusion criteria are fulfilled.

### **5.3.2.3 Restrictions**

Study restrictions are explained in Section 2.3 and prohibited concomitant treatments are explained in Section 2.3.1.

### **5.3.3 Module 2: Ascending Combination MAD**

Module 2 will enroll three patients into a cohort with follow up for AEs and DLT.

Patients will start with a single dose of RXC004 followed by a washout of 3-7 days (Cycle 0). RXC004 and nivolumab will commence at Cycle 1. The first cohort will be daily RXC004 and 480 mg nivolumab every 4 weeks (28 days).

The DLT period will be until the end of Cycle 1. Dose escalation will continue in a 3+3 design until MTD/MFD has been reached in the combination. Decisions on doses and/or schedules of RXC004 in combination will be made in discussion with the SRC.

### **5.3.4 Selection of Doses for Module 2**

In Module 2, the starting dose of RXC004 will be at a lower dose than the highest confirmed safe and tolerated dose from the ongoing monotherapy study (Module 1). The RXC004 dose used in Module 2 will not be escalated to exceed the MTD for RXC004 in monotherapy (2mg RXC004 QD).

Nivolumab will be administered at 480mg q4w, which is an approved dose and regimen from the nivolumab prescribing information. The dose of nivolumab will not be modified in this module.

### **5.3.5 Selection and Timing of Dose for Each Subject**

The doses and duration of treatment for Module 2, is detailed below. The exact times the study drug was administered and comments are to be recorded directly on the appropriate page of the CRF.

#### **5.3.5.1 Dose Regimen**

Module 2 will start with a continuous dose of RXC004 that is lower than the highest confirmed safe and tolerated dose from the ongoing monotherapy study (Module 1).

All patients will start with a single RXC004 dose in Cycle 0, followed by a 3-7 day washout. Nivolumab will commence on Cycle 1, Day 1 concurrently with daily RXC004. Cycle 1 onwards will be 28 days in length.

The RXC004 and nivolumab combination dose escalation will start with continuous dosing of RXC004, but based on emerging data the SRC may decide to propose the exploration of intermittent combination schedules.

**5.3.5.2 The nivolumab dose and regimen selected for this study are based on the approved prescribing information for nivolumab. The recommended dosage for nivolumab is 240 mg Q2W or 480 mg Q4W. 480 mg Q4W has been selected to complement a 28-day cycle of RXC004 and reduce the number of patient visits required. If a patient continues in the study on nivolumab alone, this treatment may be continued for a maximum of 12 months in total. Dose-Escalation Plan**

The dose-escalation scheme will not exceed doubling of the dose.

Dose, frequency and schedule in subsequent cohorts may increase or decrease in response to safety, tolerability, pharmacokinetic and emerging non-clinical data. The RXC004 dose used in Module 2 will not be escalated to exceed the MTD for RXC004 in monotherapy (2mg RXC004 QD).

After each dose level during the dose escalation phase of the study, a SRC will evaluate the safety and tolerability and pharmacokinetics of RXC004 in combination with nivolumab to decide the next dose and/or schedule.

Table 5 shows an indicative dose escalation scheme for Module 2. All dose levels beyond cohort 1 may change in light of emerging safety, tolerability, and pharmacokinetic data, and also evolving relevant pre-clinical data.

**Table 5 Indicative Dose Escalation Scheme for Module 2**

Planned Dose levels	RXC004 Dose (Starting Cycle 0)	Nivolumab Dose/Regimen (Starting Cycle 1)
1	1 mg QD	480mg q4w
2	1.5 mg QD	480mg q4w
3	2 mg QD	480mg q4w

Note: This indicative dose and schedule optimisation scheme is subject to SRC recommendation.

The pre-clinical toxicology data supports continuous dosing of RXC004 in humans, and Module 2 will start with this schedule. However, based on emerging data the SRC may decide to propose the exploration of intermittent RXC004 in combination with nivolumab schedules. The nivolumab dose and regimen will not be adjusted in this module.

Please see RXC004 IB and nivolumab prescribing information for further details.

### **5.3.6 Dose-Limiting Toxicity for RXC004 + Nivolumab Combination (Module 2)**

The DLT assessment period runs from the start of dosing with RXC004 and nivolumab (Cycle 1 Day 1) up to Cycle 1 Day 28 where nivolumab treatment is administered every 28 days starting on C1D1.

A DLT is defined as an AE or abnormal laboratory value that occurs from cycle 1 day 1 up to Cycle 1 Day 28, assessed as unrelated to disease progression, intercurrent illness, or concomitant medications and is possibly related to RXC004, nivolumab or both agents and that despite optimal therapeutic intervention meets any of the following criteria;

1. Haematological toxicity that is:
  - $\geq$  CTCAE grade 4 neutropenia present for more than 4 consecutive days
  - Grade 3 neutropenia ( $ANC \geq 500$  to  $< 1000$  cells/mm^3) of any duration accompanied by fever  $\geq 38.5^{\circ}C$  and/or systemic infection
  - Grade 3 thrombocytopenia ( $25,000$  to  $< 50,000/mm^3$ ) with clinical evidence of bleeding
2. Any other confirmed haematological toxicity  $\geq$  CTCAEv4 grade 4 (a repeat may be required for confirmation of an isolated abnormality in the absence of clinical signs, symptoms or other abnormal investigations, i.e. a suspected spurious value)
3. Non-haematological toxicity  $\geq$  CTCAE grade 3 including:

- Laboratory abnormalities that are considered clinically significant by the investigator (with or without clinical symptoms or signs)
  - QTc prolongation (> 500 msec or 60 msec above baseline)
4. Any other toxicity that:
    - Is greater than that at baseline, is clinically significant and/or unacceptable, and is judged to be a DLT by the SRC
    - Is a protocol defined stopping criteria and is suspected to be RXC004 or Nivolumab related
  5. Any grade 3 or higher immune-related adverse events

A DLT excludes:

1. Inadequately treated grade  $\leq 3$  nausea and/or vomiting and grade  $\leq 3$  diarrhoea
2. Any toxicity clearly unrelated to RXC004 and/or Nivolumab e.g. solely related to the disease or disease-related process under investigation.
3. Isolated laboratory changes of any grade without clinical sequelae or clinical significance

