#### Cohort Expansion

If one patient experiences a DLT in a group of 3 or more evaluable patients, then the cohort will be expanded to include 6 evaluable patients. Note: cohort expansion to more than 3 patients per cohort ( $\geq 4$  patients) may occur also if more than 3 patients are screened in a single cohort and are deemed eligible; in such cases dose escalation to the next higher dose will not occur until all patients (e.g. 3 or 4 patients) have completed the DLT assessment period with no DLT observed. If only one DLT is observed in the complete cohort of 6 evaluable patients, then dose escalation may occur, once all patients in the expanded cohort have completed their first cycle of treatment with RXC004. If 2 or more patients experience a DLT in a group of up

to 6 evaluable patients (including those in the dose expansion arms), irrespective of the number of patients enrolled, the dose will be considered not tolerated and recruitment to the cohort and dose escalation will cease. A lower, intermediate dose (de-escalation) may be considered in order to better define the MTD.

The highest dose where  $\leq 1$  DLT is seen in 6 patients will be termed the MTD.

If a patient becomes unevaluable following dose administration they may be replaced, if required, to ensure at least 3 patients are evaluable for an assessment of safety and tolerability at that dose. There will be no minimum time period required between completion of dosing in the last evaluable patient from one cohort and the start of dosing in the subsequent cohort.

After each dose level during the dose escalation phase of the study, a SRC will evaluate the safety and tolerability and pharmacokinetics of RXC004 to decide the next dose and/or schedule.

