## **5.2.3 Ascending Monotherapy SAD/MAD**

Module 1 will commence with an accelerated dose-escalation schedule and enrol three patients into a cohort with follow-up for AEs and DLT.

Patients will receive a single dose of RXC004 on Day 1 followed by a 6-10 days' washout period (Cycle 0) [this washout period may change based upon emerging data]. Cycles of 21

[figure not shown]
days of multiple dosing will then begin until the patient is withdrawn from the study (Cycle 1 onwards).

Dose escalation will continue in a 3+3 design until MBAD (as defined in Section 3.1.5) has been found to be tolerated. Subsequent dose escalation will continue in a 3+3 design until MTD/MFD has been reached.

The decision to dose escalate will be made upon the assessment of the safety and tolerability data collected up until the time of study drug administration on Cycle 2, Day 1. This DLT assessment period was selected as any acute toxicities leading to cessation of dose escalation in this study are anticipated to present within this duration. Doses and/or schedules of RXC004 will be defined by the SRC.

Optional skin-punch biopsies will be taken from all patients in Module 1 at baseline and while receiving treatment for analysis of pharmacodynamic markers of Wnt pathway inhibition (see Schedule of Assessments in Appendix 1).

**Figure 4** Module 1 RXC004 monotherapy SAD/MAD

- SRC approval for next cohort escalation or expansion required.
- In this example schematic diagram MBAD is achieved following the completion of Cohort 1
- Single dose of RXC004 following by a washout period of 6-10 days (Cycle 0) then 21 days' continuous dosing (Cycle 1 onwards) until withdrawal.

In Module 1, MBAD will be defined using either PK or pharmacodynamic data.

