### 5.2.6 Dose-Limiting Toxicity for Module 1 (RXC004 Monotherapy)

The DLT assessment period runs from the start of dosing with RXC004 (Cycle 0 Day 1) up to Cycle 1 Day 21 for patients enrolled in Module 1.

A DLT is defined as an AE or abnormal laboratory value that occurs from the first dose of study treatment up to Cycle 1 Day 21, assessed as unrelated to disease progression, intercurrent illness, or concomitant medications that despite optimal therapeutic intervention meets any of the following criteria:

1. Haematological toxicity that is:
  - CTCAE  $\geq$  Grade 4 present for more than 4 consecutive days
  - Grade 3 neutropenia (ANC  $\geq$  500 to  $<$  1000 cells/mm^3) of any duration accompanied by fever ( $\geq$  38.5°C) and/or systemic infection
  - Grade 3 thrombocytopenia (25,000 to  $<$  50,000/mm^3) with clinical evidence of bleeding
2. Any other confirmed haematological toxicity CTCAE  $\geq$  Grade 4 (a repeat may be required for confirmation of an isolated abnormality in the absence of clinical signs, symptoms or other abnormal investigations, i.e. a suspected spurious value)
3. Non-haematological toxicity CTCAE  $\geq$  Grade 3 including:

- Laboratory abnormalities that are considered clinically significant by the investigator (with or without clinical symptoms or signs)
  - QTc prolongation ( $> 500$  msec or 60 msec above baseline)
4. Any other toxicity that:
- Is greater than that at baseline, is clinically significant and/or unacceptable, and is judged to be a DLT by the SRC
  - Is a protocol defined stopping criterion and is suspected to be RXC004 related
  - Results in an interruption of dosing schedule of more than 14 days

A DLT excludes:

1. Inadequately treated  $\leq$ Grade 3 nausea and/or vomiting and  $\leq$ Grade 3 diarrhoea
2. Any toxicity clearly unrelated to RXC004 e.g. solely related to the disease or disease-related process under investigation
3. Isolated laboratory changes of any grade without clinical sequelae or clinical significance

The incidence and type of DLT-type toxicity emerging from treatment beyond Cycle 1 Day 21 will be taken into account by the SRC in determining dose-escalation steps.

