**Appendix 2 Schedule of Assessments - Module 2**

	Module 2 (RXC004 + Nivolumab) Schedule of Assessments										
	Pre-Screening	Screening	Cycle 0 (3-7 days)	Cycle 1 (28 day cycle)		Cycle X Day 1 (28 day cycles)	IP Discontinuation	30 day Safety Follow-up 	90 day Safety Follow-up 	PFS Follow-up	
Window	n/a	-28 to -1	D1	D1	D15 +/- 1d	+/- 3d	Within 7 days of discontinuation	+/- 3d	+/- 3d		
Pre-Screening informed consent (optional)	X										
Diagnostic / Archival tumour tissue (optional)	X										
Genetic screening for RNF43/RSPO aberrations (optional)	X										
Informed consent		X									
Pharmacogenetics (optional consent and blood sample) 		X									
Demography & baseline characteristics		X									
Smoking status & alcohol consumption		X									
Medical/surgical history		X									
Inclusion/exclusion criteria**		X									
Bone Scan		X	As clinically indicated								

Module 2 (RXC004 + Nivolumab) Schedule of Assessments										
	Pre-Screening	Screening	Cycle 0 (3-7 days)	Cycle 1 (28 day cycle)		Cycle X Day 1 (28 day cycles)	IP Discontinuation	30 day Safety Follow-up l	90 day Safety Follow-up l	PFS Follow-up
Window	n/a	-28 to -1	D1	D1	D15 +/- 1d	+/- 3d	Within 7 days of discontinuation	+/- 3d	+/- 3d	
HepB, HepC and HIV testing		X								
Physical examination a		X	X	X		X	X			
ECOG/WHO performance status		X	X	X		X	X			
Pregnancy test (WOCBP only)		(X)	(X)	(X)		(X)				
Vital signs (including height and weight) b		X	X	X	X	X	X	X		
Clinical chemistry / Haematology		X	X	X	X	X	X	X	X	
TSH (reflex T3/T4) m		X		X	X	X	X	X	X	
Urinalysis*		X	X	X	X	X				
ECG		X	X	X	X	X h	X			
DXA scan (including VFA*** at baseline)		X				Cycle 2, 4 and 7, and every third cycle thereafter				
Tumour biopsy (optional - archive or newly acquired)		X			X g	X g				
Blood samples for bone turnover biomarkers		X			X	X	X			
Blood sample for circulating soluble factors c			X		X	X				

Module 2 (RXC004 + Nivolumab) Schedule of Assessments											
	Pre-Screening	Screening	Cycle 0 (3-7 days)	Cycle 1 (28 day cycle)		Cycle X Day 1 (28 day cycles)	IP Discontinuation	30 day Safety Follow-up l	90 day Safety Follow-up l	PFS Follow-up	
Window	n/a	-28 to -1	D1	D1	D15 +/- 1d	+/- 3d	Within 7 days of discontinuation	+/- 3d	+/- 3d		
Blood sample for PBMC (viable cells) c			X		X	X					

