**Footnotes - General**

Assessments made on Day 1 of each cycle are to be conducted prior to RXC004 administration, unless specified otherwise.

Additional assessments may be conducted as clinically indicated.

A tolerance of +/-1 day will be permitted for all study visits and a tolerance of -1 day for all assessments relative to the study visit, unless specified otherwise.

\* Female patients, if fertile, will require a serum pregnancy test at Screening and urine pregnancy on Day 1 of each cycle

\*\*Eligibility criteria to be re-checked at Cycle 1 prior to dose administration.

\*\*\*A lateral T & L spine assessment if a Vertebral Fracture Assessment (VFA) cannot be completed locally

- a A full physical examination is required at Screening and prior to Day 1 of each cycle ; Symptom-directed physical examination is acceptable at other time-points
- b Vital signs (heart rate, BP, temperature and respiration rate) will be assessed pre-dose and up to 1 hour after the RXC004 administration. Patient status will be monitored during RXC004 administration and repeat vital signs will be taken if needed. Height is required at screening only. Weight will be recorded at Screening and on Day 1 of each cycle.
- c Pre-first dose on Cycle 0 Day 1 and 4-6hrs post dose on Cycle 1 Day 15 and Day 1 of each subsequent cycle
- d Fresh blood samples to be collected from selected sites only (in close proximity to RedX laboratory). All samples should be collected pre-dosing.
- e Pre-first dose on Cycle 0 Day 1 and 4-6hrs post dose on Day 1 of each subsequent cycle and at progression/discontinuation
- f Patients will have PK blood sampling conducted at the following sample times  
 Cycle 0: Day 1 - Predose, then 30 mins, 1 h, 2 h, 4 h, 6 h, 8 h, 10 h, 12 h, 24 h, and 48 h post-dose.  
 Cycle 1, Day 15: Predose, then 30 mins, 1 h, 2 h, 4 h, 6 h, 8 h, 10 h, 12 h & 24 h  
 Cycle X, Day 1 - A single pre-dose sample will also be taken on subsequent samples on Day 1.  
 The SRC may advise on adjusted time-points. The actual time for each blood draw must be accurately recorded.
- g An optional 'on treatment' biopsy at C1D15 and during Cycle 3 of treatment, preferably from the same site as the baseline biopsy sample
- h On Cycle 0, Day 1 and Cycle 1, Day 1 a resting 12-lead ECG will be conducted pre-dose and 30 mins (+/- 15 mins) after RXC004 administration. On Day 1 of all other cycles, a resting 12-lead ECG will be conducted pre-dose only.

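### On the nominal Module 2 schedule the DLT period closes one day before the pre-dose Cycle 2 Day 1 tests, so whether a finding counts in the 3+3 depends on the appointment date

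*Protocol*

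**What the plan says.** **Module 2.** Protocol 5.3.6 counts as a DLT an adverse event or abnormal laboratory value that "occurs from cycle 1 day 1 up to Cycle 1 Day 28". Section 5.3.3 agrees: "The DLT period will be until the end of Cycle 1". Appendix 2 schedules chemistry, haematology and ECG at Cycle 1 Day 1, at Cycle 1 Day 15 (+/- 1 day) and then on Day 1 of each later 28-day cycle (+/- 3 days). Its general footnotes say that "Assessments made on Day 1 of each cycle are to be conducted prior to RXC004 administration" and allow assessments to be done one day before the visit. Footnote k asks for chemistry, haematology and thyroid results, within 3 days, before an infusion starts.

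**Module 1.** Section 5.2.6 defines a DLT as something that "occurs from the first dose of study treatment up to Cycle 1 Day 21". Section 5.2.3 bases the escalation decision on "safety and tolerability data collected up until the time of study drug administration on Cycle 2, Day 1" and calls that span the DLT assessment period. Section 5.2.6 also says that the Safety Review Committee (SRC) will take account of DLT-type toxicity arising after Cycle 1 Day 21. Section 5.3.6 has no such sentence for Module 2.

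**Counting rule.** Under 3.1.3 a dose is not tolerated when 2 or more of up to 6 evaluable patients have a DLT. Under 3.2 and 4.3.1 the SRC is permitted, but not required, to weigh later events that meet the DLT definition. SAP VI.J.4 refers to a DLT in Cycle 0 and/or Cycle 1 and does not mention C2D1.

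**The concern.** The C2D1 tests are done before RXC004 dosing, and the pre-infusion laboratory results must be reviewed before nivolumab is given. What they show therefore comes from Cycle 0 and Cycle 1 treatment, which is the exposure that the DLT period is meant to judge. On the nominal schedule they carry a date one day after the period has closed. A clinically significant Grade 3 liver enzyme rise, a confirmed Grade 4 cytopenia or a QTc prolongation that arises after Day 15 and is first recorded at C2D1 would then be left out of the count.

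The 3+3 rule turns on single events. One DLT more or less decides between escalating (0/3) and expanding (1/3), and between tolerated (1/6) and not tolerated (2/6). Defining doses for further evaluation is part of the primary objective, so whether an event counts should not depend on which day within a permitted window the patient attended.

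**Working it through.** No power, alpha or sample-size figure is involved, so there is nothing of that kind to reproduce. The check is a day count, followed by an illustration on assumed values.

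**1. Nominal schedule, Module 2.** The cycle has 28 days, so C2D1 = 28 + 1 = Day 29. The DLT period ends on Day 28. The difference is one day.

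**2. Permitted visit days.** Day 29 +/- 3 gives Days 26 to 32. Days 26, 27 and 28 (3 of 7) lie inside the DLT period and Days 29 to 32 (4 of 7) lie outside.

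**3. Early assessments.** The last column reads footnote k as accepting a blood sample from up to 3 days before the infusion, which is an assumption about its wording.

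| C2D1 visit | Tests on the visit day | Tests one day early | Bloods 3 days early |
|---|---|---|---|
| Day 26, 27 or 28 | inside | inside | inside |
| Day 29 | outside | inside (Day 28) | inside (Day 26) |
| Day 30 | outside | outside (Day 29) | inside (Day 27) |
| Day 31 | outside | outside (Day 30) | inside (Day 28) |
| Day 32 | outside | outside (Day 31) | outside (Day 29) |

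Even for a visit exactly on Day 29, the same abnormality is inside or outside according to when the sample was drawn.

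**4. Gap between scheduled tests.** The Cycle 1 Day 15 visit falls on Days 14 to 16, which leaves 28 - 16 = 12 to 28 - 14 = 14 days of the period before C2D1 without a scheduled laboratory test or ECG.

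**5. Overlap at the early end.** With C2D1 on Day 26, Cycle 2 and the second infusion (q4w +/- 3 days, footnote k) begin while the DLT period still has Days 27 and 28 to run.

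**6. Module 1.** Section 5.2.3 ends the period at dosing on C2D1 (Day 22 of a 21-day cycle) and 5.2.6 ends it on Day 21. The two cannot both apply to a finding made before dosing on Day 22.

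**7. Illustration only.** Let p be the true DLT probability and f the share of DLTs seen only at C2D1 and not counted. The documents give neither. For cohorts of 3 expanded to 6, the probability of escalating is P(q) = (1-q)^3 + 3q(1-q)^2 × (1-q)^3, with q = p if everything counts and q = p(1-f) if not. For p = 0.33 and f = 20%, q = 0.264 and P = 0.399 + 0.171 = 0.570. With everything counted, P = 0.434.

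| p | all counted | f = 10% | f = 20% | f = 30% |
|---|---|---|---|---|
| 0.20 | 0.709 | 0.752 | 0.793 | 0.834 |
| 0.33 | 0.434 | 0.500 | 0.570 | 0.641 |
| 0.50 | 0.172 | 0.234 | 0.309 | 0.396 |

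For each assumed p and f, the shift from the second column is an upper bound, because the SRC may act on the finding anyway.

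**The case against.** The best defence has four parts.

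- **The definition turns on when toxicity occurs, not on when it is measured.** A finding made before dosing on C2D1 could be dated to Cycle 1. That is fair, but the protocol gives no rule for dating an abnormality first detected at C2D1, so the reading is possible but not secured.
- **The tolerances can bring the closing tests inside the period.** This is true and rules out any claim that C2D1 findings are always excluded. It also means that identical results can be treated differently.
- **Other safeguards exist.** Adverse events are recorded at least weekly (7.2), and unscheduled tests are allowed when clinically indicated. Isolated laboratory changes without clinical significance are not DLTs. Although 3.1.2 says "There will be no minimum time period required between completion of dosing in the last evaluable patient from one cohort" and the start of the next, it makes escalation wait for the DLT period to be completed, and for the first cycle in an expanded cohort. The SRC may defer a decision and may weigh Cycle 2 events. What is exposed is therefore narrow: a clinically significant but silent abnormality arising after Day 15 and first recorded after Day 28. For Module 2, however, SRC consideration is optional and stands outside the 2-of-6 count. Section 4.1 also makes a laboratory or ECG deterioration an adverse event only if it is serious, a DLT or a reason for stopping, so a finding that is not a DLT may not reach the SRC as an event. Section 7.2.2, which treats clinically significant laboratory abnormalities as adverse events, pulls the other way.
- **It is late to change.** Module 1 is complete (5.4) and its database is locked (SAP I). SAP Table 2 lists the third Module 2 level as N/A. This limits the effect on escalation, but the SAP still tabulates DLTs for both modules.

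A reader might take the 13 days from Day 16 to Day 28 (13/28 = 46%) as the share of DLTs missed. It is only the interval between scheduled tests and says nothing about how many events first appear at C2D1.

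**Conclusion.** The point holds for Module 2 as a boundary defect. On the nominal schedule the period closes one day before the tests that reflect its last two weeks, and across the permitted window the status of a finding depends on the appointment or sampling date. In Module 1 it is a contradiction between 5.2.3 and 5.2.6, softened by the statement that later toxicity will be taken into account. It should not be described there as a stretch of Cycle 1 with no laboratory test that counts, because under 5.2.3 the C2D1 tests do count.

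A reader might also infer that DLT rates are materially understated and that the combination MTD is set too high. The documents do not support that. They give no share of DLTs first seen at C2D1, the SRC can act on such events, and Module 2 may not exceed 2 mg QD in any case. What can be said is that one finding of this kind is enough to turn 1/3 into 0/3, or 2/6 into 1/6. The conclusion rests on reading the date limits literally, and on C2D1 being the next scheduled laboratory and ECG visit after Day 15 for a patient still on treatment.

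**What to change.** - Reconcile Protocol 5.2.3, 5.2.6, 5.3.3 and 5.3.6 and the DLT definition in SAP VI.J.4, so that findings at the pre-dose C2D1 assessments count toward the DLT evaluation in both modules, as 5.2.3 already provides for Module 1.
- State that the SRC reviews those results before it decides on escalation.
- For completed cohorts, list and flag beside the DLT table any DLT-grade finding first seen at C2D1. The reported DLT counts can then be read with and without them.
- State how the +/- 3-day window in Appendix 2 and the 28-day DLT period fit together. These passages must be reconciled. No change to the visit or infusion window is proposed here.

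The cost is wording in four protocol sections and the SAP, plus one flagged listing. The assessments are already scheduled. Slightly more DLTs may be counted, and a cohort decision may wait a few days: at most 32 - 28 = 4 days beyond Day 28 if C2D1 falls at the end of its window.
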